### 13.2. Ethical Review

Lilly or its representatives must approve all ICFs before they are used at the investigative sites. All ICFs must be compliant with the ICH guideline on GCP.

Documentation of ERB approval of the protocol and the ICF must be provided to Lilly before the study may begin at the investigative sites.

The study site's ERBs should be provided with the following:

- the current IB or package labeling and updates during the course of the study
- the ICF
- relevant curricula vitae.

### 13.3. Regulatory Considerations

This study will be conducted in accordance with:

- consensus ethics principles derived from international ethics guidelines, including the Declaration of Helsinki and Council for International Organizations of Medical Sciences International Ethical Guidelines
- International Conference on Harmonisation (ICH) GCP Guideline (E6)
- applicable laws and regulations.

The investigator or designee will promptly submit the protocol to applicable ERB(s).

Some of the obligations of Lilly will be assigned to a third-party organization (TPO).

An identification code assigned by the investigator to each patient will be used in lieu of the patient's name to protect the patient's identity when reporting AEs and/or other trial-related data.

### **13.3.1. Investigator Information**

Site-specific contact information may be provided in a separate document.

Physicians with a specialty in oncology will participate as investigators in this clinical trial.

### **13.3.2. Protocol Signatures**

The sponsor's responsible medical officer will approve the protocol, confirming that, to the best of his or her knowledge, the protocol accurately describes the planned design and conduct of the study.

After reading the protocol, each principal investigator will sign the protocol signature page and send a copy of the signed page to a Lilly representative.

### **13.3.3. Final Report Signature**

The CSR coordinating investigator will sign the final CSR for this study, indicating agreement that, to the best of his or her knowledge, the report accurately describes the conduct and results of the study.

Lilly will select an investigator to serve as the CSR coordinating investigator.

The Lilly responsible medical officer and statistician will sign/approve the final CSR for this study, confirming that, to the best of his or her knowledge, the report accurately describes the conduct and results of the study.

**Attachment 1. Protocol JPBQ Study Schedule**

---

Study Schedule, Protocol I3Y-CR-JPBQ

Perform procedure as indicated.

		Baseline		Patients on Study Treatment							Postdiscontinuation Follow-Up		
		BL		1	2			3	4 – X		Short-Term Follow-Up a	Long-Term Follow-Up a	
		0		1	2			3	4 – X		801	802 - 8XX	
		≤28	≤14	1	15 ± 3	1 b	15 ± 3	last 7 days	1 b	1 b	last 7 days		
Procedure Category	Procedure	Protocol Reference											
Study Entry/ Enrollment	Informed Consent Form signed (prior to performance of any protocol-specific tests/procedures) c	Section 8.1		X c									
	Inclusion/Exclusion evaluation	Section 7			X								
Medical History	Initial history/preexisting conditions/ previous treatment	Section 12.2.3			X								
Physical Examination (Obtain prior to drug administration for on-therapy cycles)	Height	Section 12.2.3			X								
	Weight	Section 12.2.3			X	X		X		X	X		X
	Vital Signs (Temp, BP, HR, RR)	Section 12.2.3			X	X		X		X	X		X
	ECOG performance status	Section 7.1 Attachment 4			X	X		X		X	X		X
Tumor Assessment	Tumor measurement (palpable or visible) d	Section 10.1.1			X d				X d	X d		X d	X d
	Radiologic imaging according to RECIST e	Section 10.1.1 Attachment 5			X e				X e		X e	X e	X e
	Bone Scintigraphy f	Section 10.1.1 Attachment 5			X f						X f	X f	X f
	X-ray, or CT scan with bone windows, or MRI g	Section 10.1.1 Attachment 5			X g				X g		X g	X g	X g
Randomization h	Section 9.3			X h									
Survival information i	Section 10.1										X i	X i	

		Baseline	Patients on Study Treatment								Postdiscontinuation Follow-Up			
		BL	1	2			3	4 – X		Short-Term Follow-Up a	Long-Term Follow-Up a			
		0	1	2			3	4 – X		801	802 - 8XX			
		≤28	≤14	1	15±3	1 b	15±3	last 7 days	1 b	1 b	last 7 days			
Procedure Category	Procedure	Protocol Reference												
Adverse Event Collection/CTCAE Gradingj		Section 10.3		X j	X j	X j			X j	X j		X j	X j	
Concomitant Medication Notation		Section 9.6		X	X	X			X	X		X		
Study Diaries	Dispense Study Diaries	Section 9.7.1			X	X			X	X				
	Review/Collect Study Diaries	Section 9.7.1				X			X	X		X		
Lab/ Diagnostic Tests	Central hematology k	Attachment 2			X k	X k	X k	X k	X k	X k		X k		
	Central chemistry k	Attachment 2			X k	X k	X k	X k	X k	X k		X k		
	Local FSH and estradiol levels l	Attachment 2			X l									
	Central pharmacokinetic (PK) sampling m	Attachment 7				X m		X m		X m	X m			
	Pharmacogenetic whole blood sampling n	Section 10.4.2.1				X n								
	Biomarker plasma sample o	Section 10.4.2.2				X o		X o					X o	
	Local ECG p	Section 10.3.2.1			X p								X p	
Study Treatment	Abemaciclib/Placebo q		Section 9.1		Q12H on Days 1 through 28 of every cycle q									
	Cohort A	Anastrozole q	Section 9.1		Take 1 mg tablet orally Q24H on Days 1 through 28 q									
		Letrozole q	Section 9.1		Take 2.5 mg tablet orally Q24H on Days 1 through 28 q									
	Cohort B	Fulvestrant q	Section 9.1		Days 1 and 15 of Cycle 1, then Day 1 of Cycle 2 and beyond q									
Health Outcomes	EORTC QLQ-C30 , mBPI-sf r		Section 12.2.11			X r		X r		X r	X r		X r	
	Hospitalization		Section 12.2.11.3				X		X		X	X	X	
	Transfusion		Section 12.2.11.3				X		X		X	X	X	

Abbreviations: BL = baseline; BP = blood pressure; CT = computed tomography; CTCAE = Common Terminology Criteria for Adverse Events; ECG = electrocardiogram; ECOG = Eastern Cooperative Oncology Group; EORTC QLQ-C30 = European Organization for Research and Treatment of Cancer Quality of Life Questionnaire-Core 30; FSH = follicular stimulating hormone; HR = heart; IV = intravenous; mBPI-sf = modified Brief Pain Inventory short form; MRI = magnetic resonance imaging; NSAI = nonsteroidal aromatase inhibitor; PD = progressive disease; PK = pharmacokinetics; Q12H = every 12 hours; Q24H = every 24 hours; RECIST = Response Evaluation Criteria in Solid Tumors; RR = respiratory rate; SAE = serious adverse event; temp = temperature.

- a Short-term follow-up begins the day after the patient and the investigator agree that the patient will no longer continue study drug and lasts approximately 30 days ( $\pm 7$  days); the associated study procedures are performed once at the end of this period. Long-term follow-up begins the day after short-term follow-up is completed and continues until the patient's death or overall study completion; the associated study procedures are performed approximately every 12 weeks ( $\pm 14$  days) for the duration of this period.
- b For Cycle 2 and beyond, the start of a cycle may be delayed up to 7 days for logistical reasons and up to 14 days to allow sufficient time for recovery from toxicity possibly related to a study drug. Refer to Section 9.4.1.1.2.
- c Informed consent form is signed within 28 days prior to randomization of study drug and prior to performance of any protocol-specific tests/procedures.
- d Visible tumor (such as skin lesions) identified at baseline require repeat photographic images on Day 1 of every second cycle beginning with Cycle 3 and continuing through Cycle 19 (inclusive), on Day 1 of every third cycle after Cycle 19, and within 14 days of clinical progression. Photographic images may be taken more frequently based upon the discretion of the investigator or following the identification of new skin lesions post-baseline. Each photographic image of the tumor should include a ruler if applicable. For patients who discontinue study treatment without objectively measured PD, continue to evaluate tumor response approximately every 8 weeks for the first 12 months following randomization and thereafter approximately every 12 weeks by the same method used at baseline and throughout the study, until the patient has objective disease progression or until study completion. After the patient has objective disease progression, tumor assessments are no longer required and the patient will continue with post-discontinuation follow-up until the patient's death or overall study completion. Assessments should be performed prior to dosing at the beginning of the required cycle unless otherwise indicated.
- e For patients with inoperable locoregionally recurrent breast cancer, MRI scan of the breast is performed locally at baseline (Day -28 to Day -1), in the last 7 days of every second cycle beginning with Cycle 2 and continuing through Cycle 18, in the last 7 days of every third cycle after Cycle 18, and within 14 days of clinical progression. For all patients, CT or MRI scan of the chest, abdomen, and pelvis is performed locally at baseline (Day -28 to Day -1), in the last 7 days of every second cycle beginning with Cycle 2 and continuing through Cycle 18, in the last 7 days of every third cycle after Cycle 18, and within 14 days of clinical progression. It is recommended that CT imaging of the abdomen and pelvis be performed with IV contrast whenever possible. If this is not feasible due to hypersensitivity or other conditions, then gadolinium-enhanced MRI is preferred. For patients with known serious allergic reactions to CT contrast material, a CT of the chest without contrast and gadolinium-enhanced MRI of the abdomen/pelvis are encouraged. For patients who discontinue study treatment without objectively measured PD, continue to evaluate tumor response approximately every 8 weeks for the first 18 months following randomization and thereafter approximately every 12 weeks by the same method used at baseline and throughout the study until the patient has objective disease progression or until study completion. After the patient has objective disease progression, radiologic tests are no longer required and the patient will continue with post-discontinuation follow-up until the patient's death or overall study completion. Assessments should be performed prior to dosing at the beginning of the required cycle unless otherwise indicated.
- f Bone scintigraphy is performed locally at baseline (Day -28 to Day -1) for all patients. If available, prior bone scintigraphy (obtained as part of routine clinical care) within 45 days before Cycle 1, Day 1 is also acceptable. Bone scintigraphy should be repeated for all patients between last 7 days of every sixth

cycle beginning with Cycle 6, when complete response is identified in target disease, or when progression in bone is suspected. Importantly, RECIST v1.1 emphasizes that bone scintigraphy is not adequate to measure bone lesions; however, bone scintigraphy can be used to confirm the presence or disappearance of bone lesions. For patients who discontinue study treatment without objectively measured progressive disease (PD), continue to evaluate tumor response approximately every 6 months until the patient has objective disease progression or until study completion. After the patient has objective disease progression, bone scintigraphy is no longer required and the patient will continue with post-discontinuation follow-up until the patient's death or overall study completion. Assessments should be performed prior to dosing at the beginning of the required cycle unless otherwise indicated.

- g One or more of these studies [X-ray, CT scan with bone windows, or MRI] is performed locally at baseline (Day -28 to Day -1), in the last 7 days of every second cycle beginning with Cycle 2 and continuing through Cycle 18, in the last 7 days of every third cycle after Cycle 18, and within 14 days of clinical progression only for patients with bone lesions identified by bone scintigraphy at baseline. For patients with new lesions identified by post-baseline bone scintigraphy, targeted assessment by X-ray, CT scan with bone windows, or MRI will be performed to confirm findings. For patients who discontinue study treatment without objectively measured progressive disease (PD), continue to evaluate tumor response approximately every 8 weeks for the first 12 months following randomization and thereafter approximately every 12 weeks by the same method used at baseline and throughout the study until the patient has objective disease progression or until study completion. After the patient has objective disease progression, radiologic tests are no longer required and the patient will continue with post-discontinuation follow-up until the patient's death or overall study completion. Assessments should be performed prior to dosing at the beginning of the required cycle unless otherwise indicated.
- h The period between randomization to blinded study drug and the first dose (Cycle 1, Day 1) should not exceed 7 days.
- i Although preferable to collect during a clinic visit, survival information may be collected by contacting the patient or family directly (eg, via telephone) if no procedures are required. This should be collected at minimum every 90 days if no other procedures are performed. Additional long-term follow-up data collection will include postdiscontinuation anticancer therapies.
- j Data on SAEs that occur before the end of trial will be stored in the collection database and the Lilly Safety System. During long-term follow-up, only SAEs that are related to study drugs or protocol procedures will be collected. All adverse events possibly related to study drugs or protocol procedures should be followed until they resolve, are no longer considered to be possibly related, become stable or return to baseline, the patient starts a new therapy, the patient expires, or the patient becomes lost to follow-up. The frequency of evaluation is determined according to the judgment of the investigator.
- k Central hematology/central chemistry labs can be drawn up to 5 days prior to Day 1 of each cycle. Local hematology/local chemistry during the cycle can be performed for treatment decisions at the discretion of the investigator. If the treatment was suspended due to hematologic/non-hematologic toxicity, the decision to perform hematology and/or chemistry labs before re-initiation of the blinded study drug is at the discretion of the investigator. Assessments should be performed prior to dosing at the beginning of the required cycle unless otherwise indicated.
- l FSH and estradiol levels are required only for women age <60 years and amenorrheic for at least 12 months.
- m See PK Sampling Schedule ([Attachment 7](#)).
- n Draw sample before patient is dosed on Cycle 1, Day 1
- o During the treatment study, draw sample for all patients before dosed on Cycle 1, Day 1 and upon arrival at site on Cycle 2, Day 1. During the short-term follow-up period, draw sample only for patients discontinuing due to PD.
- p A local ECG (no replicates required) should be obtained at baseline (Day -14 to Day -1), and at the short-term follow-up visit. Patients must be resting for approximately 5 to 10 minutes before ECG collection and remain supine but awake during ECG collection.
- q Blinded study drug should be administered orally Q12H on Days 1 through 28 of each cycle; For patients in Cohort A, on Cycle 2, Day 1, patients will take

NSAI and blinded study drug at home at least 4 hours prior to arrival at the clinic. For PK purposes, NSAI should be administered at the same time (or up to 20 minutes after) the first dose of blinded study drug through Cycle 4, Day 1. Subsequently, the interval between administration of blinded study drug and NSAI may be adjusted based on the judgment of the investigator. For patients in cohort B, on Cycle 2 Day 1, patients will take the blinded study drug at home at least 4 hours prior to arrival at the clinic. For PK purposes, fulvestrant should be administered at the same time as (or up to 20 minutes after) the first dose of blinded study drug, except when specified otherwise in the PK Sampling Schedule ([Attachment 7](#)) through Cycle 4 Day 1. Subsequently, the interval between administration of blinded study drug and fulvestrant may be adjusted based on the judgment of the investigator. Fulvestrant 500 mg should be administered intramuscularly into the buttocks slowly (1 to 2 minutes per injection) as two 250-mg injections, one in each buttock; however, for patients with moderate hepatic impairment (defined as Child-Pugh Class B), including any patient who develops moderate hepatic impairment during study treatment, fulvestrant 250 mg should be administered intramuscularly into the buttock slowly (1 to 2 minutes) as one 250-mg injection.

- r EORTC QLQ-C30, mBPI-sf should be administered twice at baseline (Day -14 to Day -1, and at C1D1), Cycle 2 Day 1, and then on Day 1 of every second cycle beginning with Cycle 3 and continuing through Cycle 13, on Day 1 of every third cycle after Cycle 13, and at Short-Term Follow-Up. Patients should complete these assessments before extensive interaction with site staff.

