Patients in Cohort B will be randomized using the following stratification factors: nature of disease (visceral metastases vs. non-visceral metastases) and sensitivity to endocrine therapy (primary resistance vs. secondary resistance). The presence of visceral metastases refers to lung, liver, pleural, or peritoneal, or adrenal gland involvement at the time of randomization. Primary clinical resistance to endocrine therapy is defined as follows: 1) for endocrine therapy in the adjuvant setting, recurrence within the first 2 years of adjuvant endocrine therapy while on endocrine therapy, or 2) for endocrine therapy in the locoregionally recurrent or metastatic setting, progression within first 6 months of initiating first-line endocrine therapy while on endocrine therapy. Patients receiving prior endocrine therapy who do not meet the definition of primary clinical resistance will be considered to have secondary clinical resistance.

The primary analysis of the PFS endpoint will occur after approximately 170 PFS events have been observed in Cohort A. An interim analysis will be conducted after approximately 119 PFS events are observed to provide early efficacy information and allow for potential early communication with regulatory agencies. (see Section 12.2.6 for details).

The interim analysis of Cohort B will follow the timeline of Cohort A, which will occur only if the interim of Cohort A turns out to be positive. If patients in Cohort A continue being followed for PFS until final analysis, the final analysis of Cohort B will be conducted at the same time of Cohort A final analysis. If Cohort A stops early at interim due to efficacy, the final analysis of Cohort B may be conducted after approximately 105 PFS events have been observed in Cohort B. (see Section 12.2.14 for details).

For each cohort, all patients will be followed for progression and survival information until death or study completion, whichever occurs first.

Terms used to describe the periods during the study are defined below:

- **Baseline:** begins when the informed consent form (ICF) is signed and ends at the first study treatment dose (or at discontinuation, if no treatment is given). This may be up to 28 days prior to the first study treatment dose.
- **Study Period:** begins at the first study treatment and ends at study completion. The study period does not include the continued access period.

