## 10.2. Health Outcome/Quality of Life Measures

### 10.2.1. Patient-Reported Outcomes

The primary health outcomes research goal is to assess if abemaciclib combination therapy is able to impact the symptom burden and quality of life, as measured by the EORTC QLQ-C30 (Aaronson et al. 1993), and pain, as measured by the mBPI-sf.

Patient-reported questionnaires should be completed by patients when a language translation is available in which the patient is fluent or literate.

At each time point identified in the Study Schedule ([Attachment 1](#)), a paper copy of the mBPI-sf and the EORTC QLQ-C30 questionnaires should be administered to the patient prior to extensive interaction with site staff and study drug administration.

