#### **12.2.11.2. Pain Intensity**

Individual pain items on the mBPI-sf (ie, worst, least, average, and current pain) will be described using descriptive statistics (eg, n, mean, median, standard deviation, minimum, and maximum) by treatment arm and time points. A mixed effects model, repeated measures model may be applied to compare between treatment arms, which may be adjusted for other covariates. Corresponding analyses will also be conducted for the mean of 7 pain interference with function items. If a patient does not complete Questions 5a through 5g on the mBPI-sf, the mean score for the 7 pain interference items will be calculated based on those answered questions when at least 4 out of 7 questions were completed (ie,  $\geq 50\%$  of the questions were answered). Separate similar analyses will be conducted using the average of the mBPI-sf/worst pain assessments associated with each cycle.

Pain analysis will be based on all randomized patients with at least 1 baseline mBPI-sf “worst pain” and 1 mBPI-sf “worst pain” score on Cycle 2 Day 1 or later.

The mBPI-sf will be administered at baseline prior to study drug dosing and the Cycle 1, Day 1 score will be treated as a baseline observation and the Day 1 score of each subsequent cycle will be attributed to the previous cycle. The mBPI-sf will be administered at treatment discontinuation and grouped with observations from the previous cycle.

Time to worsening in pain will be described using the Kaplan-Meier method and will be made between the 2 treatment arms by a log-rank test. “Worsening” will be defined as either a “worst pain” increase of  $\geq 2$  points postbaseline or an analgesic drug class increase of  $\geq 1$  level. Worsening rate at Years 1, 2, and 3 will be estimated and compared between the 2 treatment arms within each cohort. The number of events due to each criterion will be described.

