#### 6.1.2. Definitions and Conventions

**Study drug** refers to abemaciclib or placebo.

**Study treatment** refers to study drug plus NSAID/fulvestrant.

The **date of randomization** is the date the patient was randomly assigned to study treatment using the interactive web response system (IWRS).

The **date of first dose** is the date of the first dose of study drug or NSAID/fulvestrant.

The **baseline value of a safety assessment** is the last value observed prior to the first dose of study drug or NSAI/fulvestrant.

The **baseline value of an efficacy assessment** is the last value observed prior to the date of randomization. If a patient's first assessment occurs after randomization but prior to the first dose, this assessment will be used as the baseline.

The **study day of a safety event or assessment** will be calculated as:

- the difference between the date of the event or assessment and the date of first dose plus 1 for all events or assessments occurring on or after the day of first dose. For example, if an event occurs on 08JUN2014 and the date of first dose was 06JUN2014, the study day of the event is 3.
- the difference between the date of the event or assessment and the date of first dose for all events or assessments occurring before the day of first dose. For example, if an event occurs on 05JUN2014 and the date of first dose was 06JUN2014, the study day of the event is -1.

The **study day of an efficacy event or assessment** will be calculated as:

- the difference between the date of the event or assessment and the date of randomization plus 1 for all events or assessments occurring on or after the date of randomization.
- the difference between the date of the event or assessment and the date of randomization for all events or assessments occurring before the date of randomization.

One **month** is defined as 365/12 days.

Unless otherwise noted, **summaries of continuous variables** will include a mean, median, standard deviation, minimum, and maximum.

Unless otherwise noted, **summaries of categorical variables** will include the frequency and percentage (relative to the population being analyzed) of each category.

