### **6.8.2. Quality of Life**

Data from the EORTC QLQ-C30 (Aaronson et al. 1993) instrument will be scored as described by the European Organization for Research and Treatment of Cancer (EORTC) scoring manual (Fayers et al. 2001).

A mixed effects, repeated measures model will be applied to compare treatment arms by cycle with respect to each instrument. The model will include baseline score as a covariate and an unstructured covariance matrix will be utilized. The analysis will include all cycles for which at least 25% of patients in each arm have an assessment.

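### The patient-reported outcome models use one baseline score and no randomisation factors, although two pre-dose scores are collected and the baseline rule for them is not named

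*Protocol*

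**What the plan says.** **Collection.** Protocol Attachment 1, footnote r, states that both questionnaires "should be administered twice at baseline (Day -14 to Day -1, and at C1D1". Protocol 10.2.1 adds that they "should be administered to the patient prior to extensive interaction with site staff and study drug administration", so the Cycle 1 Day 1 (C1D1) score is drug-free. Protocol 8.1 defines a baseline period that "begins when the informed consent form (ICF) is signed and ends at the first study treatment dose", which contains both assessments.

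**Which score is baseline.** For the mBPI-sf, Protocol 12.2.11.2 says that "the Cycle 1, Day 1 score will be treated as a baseline observation". No protocol section selects a score for the QLQ-C30. SAP 6.1.2 has two rules:
- The efficacy baseline "is the last value observed prior to the date of randomization", with the exception "If a patient's first assessment occurs after randomization but prior to the first dose, this assessment will be used as the baseline".
- The safety baseline "is the last value observed prior to the first dose of study drug or NSAI/fulvestrant".

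Health outcomes have their own section, SAP 6.8, separate from efficacy (6.7) and safety (6.10). SAP 6.8 refers to neither rule.

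**The model.** SAP 6.8.2 (QLQ-C30) states: "The model will include baseline score as a covariate". It specifies an unstructured covariance matrix and comparisons by cycle. SAP 6.8.3 repeats this for the mBPI-sf. Neither section names a stratification factor. SAP 6.7 lists each cohort's factors for the efficacy analyses, and Protocol 12.2.11.2 leaves covariate adjustment of the pain model optional and unspecified. The QLQ-C30 serves a secondary objective and the mBPI-sf an exploratory one.

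**The concern.** The trial collects a second pre-dose score that the stated model does not appear to use. It also randomises within strata that the model does not include. A single questionnaire score is a noisy covariate. Two scores predict follow-up better, and prognostic strata remove further residual variance. Both are available at no extra data cost.

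There is also a gap in definition. Two programmers working from the SAP could choose different baselines for the same patient, one using the efficacy rule and the other the safety rule. That choice affects the model covariate. It also affects maximum change from baseline (Protocol 12.2.11), time to pain worsening (Protocol 12.2.11.2) and the proportion of patients with a worst-pain increase of 2 points or more (SAP 6.8.1).

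**Working it through.** **Step 1: which score each rule picks.** Randomisation may precede the first dose by up to 7 days (Protocol 9.3, SAP 5.3), so C1D1 falls on or after the randomisation date.

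| Rule | Score selected |
|---|---|
| SAP 6.1.2, efficacy | Last score before the randomisation date; C1D1 only if it is the patient's first assessment |
| SAP 6.1.2, safety | Last score before first dose, so C1D1 |
| Protocol 12.2.11.2 (mBPI-sf only) | C1D1 counts as a baseline observation; the Day -14 to Day -1 score is not excluded |
| Protocol, QLQ-C30 | No selection made |

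The two SAP rules therefore give different answers for a patient who completes both questionnaires.

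**Step 2: precision from the second score.** The documents give no standard deviation, correlation or power for any patient-reported outcome, so there is no plan figure to reproduce. As a simplification of the mixed model, take covariance analysis at one post-baseline visit. Let ρ be the correlation of each pre-dose score with follow-up, and r the correlation between the two pre-dose scores (reliability). Both are assumptions.

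- One baseline: residual variance is proportional to 1 - ρ².
- Mean of two: residual variance is proportional to 1 - 2ρ²/(1 + r).

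Example with ρ = 0.5, r = 0.6: (1 - 0.5/1.6)/(1 - 0.25) = 0.6875/0.75 = 0.917. The standard error (SE) ratio is √0.917 = 0.957.

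| ρ | r | Variance ratio | SE ratio |
|---|---|---|---|
| 0.5 | 0.6 | 0.917 | 0.957 |
| 0.5 | 0.7 | 0.941 | 0.970 |
| 0.5 | 0.8 | 0.963 | 0.981 |
| 0.6 | 0.6 | 0.859 | 0.927 |
| 0.6 | 0.7 | 0.901 | 0.949 |
| 0.6 | 0.8 | 0.938 | 0.968 |

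Simulation with 200 and 100 patients (4,000 runs) gave variance ratios of 0.923 against 0.917 at (0.5, 0.6), and 0.913 against 0.901 at (0.6, 0.7). Over a wider grid the SE gain runs from 0.5% (ρ = 0.4, r = 0.9) to 9% (ρ = r = 0.7).

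**Step 3: precision from the strata.** If the factors explain a share R² of residual variance (assumed), the SE ratio is √(1 - R²). R² = 1% gives 0.995, and R² = 5% gives 0.975.

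**Step 4: both together, on the outcome scale.** For ρ = 0.5 and r = 0.8 to 0.6, the products are 0.981 × 0.995 = 0.976 and 0.957 × 0.975 = 0.933. With one baseline and no missing data:
- Cohort A (200 vs 100): SE = √(0.75 × (1/200 + 1/100)) = 0.106 SD, falling to between 0.104 and 0.099.
- Cohort B (100 vs 50): SE = √(0.75 × (1/100 + 1/50)) = 0.150 SD, falling to between 0.146 and 0.140.

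**Step 5: why averaging should stay inside the model.** Worst pain is scored in whole numbers from 0 to 10, and worsening is a rise of at least 2. Pre-dose scores of 3 and 4 average 3.5, so the threshold is 5.5 and the patient must score 6. With a baseline of 3 she must score 5. An averaged baseline would therefore change the endpoint itself.

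**The case against.** The case against making much of this is strong, and several parts of it stand.

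- **Contradiction.** A reader might infer that the protocol and SAP contradict each other on baseline. The protocol counts both scores as baseline and does not prefer C1D1. For the QLQ-C30 no protocol text chooses at all, so that is a gap. For the mBPI-sf a conflict arises only if the SAP efficacy rule governs; under the safety rule the documents agree.
- **Dilution.** A reader might also infer that a drug-free C1D1 score could enter as a post-baseline visit and dilute the treatment effect. The documents do not support this. Comparisons are by cycle with unstructured covariance, so a stray C1D1 value would form its own uninformative time point, and SAP 6.8 specifies no contrast pooled over visits. The protocol also requires a pain score at Cycle 2 Day 1 or later (10.2.1.2, 12.2.11.2) and a QLQ-C30 assessment after a dose (10.2.1.1). Those rules define analysis populations and do not label visits in the SAP models, so an explicit sentence is still useful.
- **Size.** Every correlation is assumed, and the top of the range is doubtful. With ρ = r = 0.6 and equally reliable follow-up scores, the implied true-score correlation is 0.6/√(0.6 × 0.6) = 1.0, meaning that patients' underlying states never diverge. The formula also assumes that both scores predict follow-up equally well. If C1D1 predicts better, the gain over C1D1 alone is smaller.
- **Strata.** The protocol already permits covariates in the pain model. Permission leaves the choice open, however, and the SAP model names none.

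**Conclusion.** This is a low-cost improvement together with a definition to settle. It is not an error that threatens a conclusion. The documents establish two scheduled pre-dose scores, two SAP baseline rules with neither assigned to these questionnaires, and models with a singular baseline score and no randomisation factors. That one score would go unused is an inference from the singular wording and the single-value rules; SAP 6.8 does not say so.

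The likely gain is a standard error about 2-4% smaller from the second score at ρ = 0.5 and reliability 0.6-0.8, and about 0.5-2.5% smaller from the strata if R² is 1-5%. These figures rest wholly on assumed values and on a single-visit simplification. No patient-reported outcome has a power target, and the PFS analyses do not depend on this point.

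**What to change.** Add to SAP 6.8, before unblinding:

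1. Include the cohort's randomisation factors in both mixed models. As main effects this adds 3 parameters in Cohort A (1 for nature of disease, 2 for prior endocrine therapy) and 2 in Cohort B (1 for nature of disease, 1 for endocrine sensitivity). Use the same data source as the stratified analyses in SAP 6.7.
2. Use both pre-dose scores in the models, as their mean or as two covariates, with the available score used if one is missing. The mean sits more easily with SAP 6.2, which rules out imputing anything but dates.
3. State that C1D1 is baseline for both instruments and is never a post-baseline visit.
4. For change scores and the 2-point worst-pain definition, name one single pre-dose score as baseline, so that the whole-number threshold is unchanged.

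The cost is SAP wording and minor programming. No new data, visits or patients are needed.
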